7.0 REGULATORY AND REPORTING REQUIREMENTS

7.1 Adverse Events (AEs)

Definition: any unfavorable medical occurrence in a human subject including any abnormal sign, symptom, or disease.

This is an observational study where diagnostic imaging and patient reported outcomes are measured in the context of routine breast cancer care. There will be no intervention that is unique to this study that does not normally occur with standard patient care. As such, there are no adverse events that are unique to this study.

Common complications associated with breast oncologic and reconstructive surgery will be tracked since we suspect that complications will be an independent risk for adversely affecting patient reported outcomes independent of tumor: breast ratio. Common complications will be obtained by reviewing the inpatient and outpatient electronic medical records in Clinical Desktop and Allscripts of all enrolled patients. We will therefore record anticipated morbidities such as anesthetic complications, bleeding, infection requiring readmission or surgery, wound healing problems requiring surgical intervention, need for re-excision in lumpectomy due to positive margins, and reconstructive failures due to flap loss or breast prosthesis explant for the purposes of this study. However, none of these are expected to be related to the performance of this study

and will not be summarized, graded or reported as traditional adverse event reporting in an interventional oncology trial.

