10.5 Data Analysis

This is a longitudinal observational study to compare effects of two treatment groups on the quality of life and to explore how the treatment effects are modified by T:B ratio. For each study patient, we have a data vector $D=(\text{group}, \text{T:B ratio}, \text{location}, Q(t), 3D(t), W)$, where group is a binary indicator for two comparison groups. T:B ratio is the tumor: breast ratio measured at a continuous scale, and location is a binary indicator of tumor location. $Q(t)$ and $3D(t)$ are Q score and the VECTRA 3D generated mammometrics respectively, measured as continuous variables at $t=(0,1,2)$, where $t=0$ is the pre-treatment baseline measurement. W is a set of patient characteristics – e.g., age, obesity, stage, etc. A longitudinal study generates correlations among the repeated measurements within the same individual, and observational study often comes with a biased estimate of the treatment comparison due to confounding. These two issues, the correlation of repeated measurements and confounding, must be taken into account in the data

analysis. Regression analyses of correlated data can simultaneously address these two issues. There are two families of statistical methods for regression analyses of correlated data – mixed effect model and generalized estimating equation (GEE). Both are appropriate for our study, even though the interpretations are different – population average vs subject specific. Data analyses for our study will be performed within this framework to adjust for the patient characteristics for unbiased comparison of treatment effect and to take into account the correlations.

10.5.1 Primary objectives:

For main effect of treatment group on Q-score: fit and test a model with Q score as the dependent variable and group as the independent variable, controlling for W in the model – (Model 1).

For the difference in Q score between two treatment groups modified by T:B ratio: fit and test a model with Q score as the dependent variable, and group, T:B ratio, and group-by-T:B ratio interaction as the independent variables, controlling for W in the model – (Model 2). The results can be better presented as a graph with two lines – Q score as a function of T:B ratio for those treated with BCT, and for those treated with Mastectomy+reconstruction.

10.5.2 Secondary objectives:

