Does tumor location impact the influence of tumor: breast ratio on patient reported outcomes following mastectomy with reconstruction or BCT?

- Add location and three way interaction term –group-by-T:B ratio-by-location into Model 2 – (Model 3). The results can be better presented as two graphs – one for each location. See Model 2 for the graph.

How does the pre and post-op Breast Q for the two groups (mastectomy + recon vs. BCT) reflect the tumor: breast ratio as calculated from 3D images rendered from MRI utilizing software-based algorithms?

- Fit and test a model with Q-score as the dependent variable and 3D image data as the independent variable with appropriate non-linear terms for 3D (e.g. spline functions), with group and possible interaction of group-by-3D (Model 4).

How does the pre and post-op Breast Q for the two groups (mastectomy + recon vs. BCT) reflect the VECTRA 3D generated mammometrics?

- Both the Breast Q and the VECTRA 3 D generated mammometrics are continuous variables. The correlation between them will be quantified by Pearson or Spearman correlation coefficient with one sample t test for population correlation coefficient =0, and with Fisher Z transformation to test the population correlation coefficient not equal to zero.

What is the impact of radiation in BCT on Breast Q (Q-score before and after

radiotherapy) and VECTRA (breast volume, nipple position, total breast skin surface area before and after radiotherapy)?

- Perform the subgroup analyses of BCT patients comparing change in outcomes of interest before and after radiation.

How do complications that arise from each scenario (mastectomy + recon) vs. BCT impact patient satisfaction?

- Fit and test a model with Q-score as the dependent variable and complication and group, and possible group-by-complication interaction as independent variables controlling for W in the model.

What is the impact of tumor location and obesity as independent determinants of patient satisfaction in the two groups (mastectomy + recon vs. BCT) relative to tumor: breast ratio?

- Fit and test a model with Q-score as the dependent variable and group, T:B ratio, location, and obesity as the independent variables, controlling for W in the model. Obtain the standardized regression coefficients for location, obesity, and T:B ratio, and compare each other to determine their relative importance.

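### The complications model omits tumor:breast ratio, so it cannot check the independence suspected in section 7.1 and could report part of a ratio effect as a complication effect

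*Combined protocol and SAP*

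**What the plan says.** Section 7.1 gives the reason for recording complications: "we suspect that complications will be an independent risk for adversely affecting patient reported outcomes independent of tumor: breast ratio".

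Section 10.5 sets out the data held on each patient. T:B ratio and location are separate elements beside W. The ratio is defined on its own ("T:B ratio is the tumor: breast ratio measured at a continuous scale"), and W is described thus: "W is a set of patient characteristics – e.g., age, obesity, stage, etc".

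The complications analysis in section 10.5.2 takes Q-score as the outcome and uses "complication and group, and possible group-by-complication interaction as independent variables controlling for W in the model". By contrast, Model 2 uses "group, T:B ratio, and group-by-T:B ratio interaction as the independent variables, controlling for W in the model", and the last secondary analysis uses "group, T:B ratio, location, and obesity as the independent variables, controlling for W in the model".

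**The concern.** T:B ratio is measured on MRI before surgery (section 6.2), so it precedes any complication and is not a consequence of one. Section 1.2 expects it to lower satisfaction after BCT and to matter less after mastectomy with reconstruction. The complications listed in section 10.2 include re-excision for positive margins, which may be more frequent when the tumor is large relative to the breast. A variable that lowers Q and also raises the chance of a complication is a confounder of the complication effect, and the planned model leaves it out.

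Two things are at stake. The independence suspected in section 7.1 cannot be examined with any planned model. And a complication effect could be reported where part of it belongs to T:B ratio. If T:B acts mainly in BCT, as the protocol expects, the distortion would fall mainly in that group and carry into the group-by-complication interaction.

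**Working it through.** **1. Which planned models hold which term (section 10.5)**

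| Analysis | Complication | T:B ratio |
|---|---|---|
| Model 1 | no | no |
| Models 2 and 3 | no | yes |
| Model 4 (3D image data) | no | no separate term |
| Correlation and radiotherapy analyses | no | no |
| Complications model | yes | no |
| Location and obesity model | no | yes |

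No row has both. Stage is named in W, but section 1.2 itself contrasts absolute tumor dimensions, which bear on staging, with the ratio. Stage is therefore at best a partial proxy.

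**2. Formula.** The plan gives no figure for this model, so there is none to reproduce. If the true complication effect is zero, the complication coefficient in BCT estimates

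spurious effect = (Q points per unit of T:B) × Δ,

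where Δ is mean T:B in BCT patients with a complication minus mean T:B in those without, given W. If T:B acts in BCT only and the two arms carry equal weight, the pooled coefficient (no interaction) is about half of this.

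**3. Inputs.** From section 10.4: 83 per arm, SD 20, 10-point threshold. Assumed, because the documents give no values:
- T:B uniform from 0.02 to 0.40, acting on Q in BCT only
- about 25% of patients with a complication
- Q falling 5 or 10 points per 0.1 of T:B
- complication odds ratio 1.5 or 2 per 0.1 of T:B
- no W in the model
- true complication effect zero

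**4. Results** (BCT arm, 4,000 simulated studies per row; without W, a model with the interaction gives the same BCT coefficient)

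| Q fall per 0.1 | Odds ratio per 0.1 | BCT effect, T:B omitted | Half of it (pooled) | BCT effect, T:B included |
|---|---|---|---|---|
| 5 | 1.5 | −2.35 | −1.2 | 0.01 |
| 5 | 2 | −3.74 | −1.9 | 0.09 |
| 10 | 1.5 | −4.74 | −2.4 | 0.03 |
| 10 | 2 | −7.57 | −3.8 | 0.07 |

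The rows agree with the formula. The implied Δ is 2.35/50 = 0.047 and 4.74/100 = 0.047 at odds ratio 1.5, and 3.74/50 = 0.075 and 7.57/100 = 0.076 at odds ratio 2.

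Simulating both arms directly gives, to within simulation error:
- pooled coefficient about −1.2 to −3.7 points, with a false-positive rate of about 6–15% at nominal 5%
- BCT-specific effect about −2.5 to −7.5 points, with a false-positive rate of about 8–28%

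**5. Sensitivity.** A second set of assumptions used 20% complications, both arms, and Q falling 5 or 10 points per SD of T:B in BCT. T:B differed by 0.25 to 0.75 SD between patients with and without complications.
- With W unrelated to T:B, the pooled spurious effect is −0.7 to −3.8 points. Check at the middle: ½ × (−10) × 0.5 = −2.5, against −2.46 simulated.
- With a W covariate correlated 0.5 with T:B, that middle value becomes −1.83, a reduction of 1 − 1.83/2.46 = 26%. The smallest value in the set is then about −0.5.
- With no T:B difference between patients with and without complications, the estimate is about 0 and rejection about 5%.
- With T:B and group-by-T:B in the model, estimates are within 0.2 of zero and rejection is about 4–5%.

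**6. Precision.** The standard error of the BCT-specific complication effect is about 5.2–5.5 points with or without the two T:B terms.

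**The case against.** The secondary objective (section 2.2, repeated in 10.5.2) asks how complications in each treatment scenario affect satisfaction. It does not ask for an effect independent of T:B ratio, and the planned model matches its wording. Where the protocol wants effects judged relative to T:B ratio, as in the last secondary objective, it says so and includes the term. This stands: the independence aim comes only from section 7.1, where it is a suspicion and not a claim. A reader might infer that the protocol asserts the independent harm as fact, or that the stated objective cannot be answered. The text supports neither. The confounding question remains, because section 10.5 itself says confounding must be dealt with.

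W is also open-ended. A reader might infer that T:B must lie outside W because other models name it beside W. That does not follow: the last secondary model names obesity beside W, although obesity is given as an example of W. The better evidence is the data vector, which lists T:B as its own element, and the fact that T:B is never placed in W.

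Finally, the size depends wholly on assumptions. The steepest slope implies a fall of 10 × 0.38/0.1 = 38 points across the assumed T:B range, or 1.9 SD. Of the listed complications, only re-excision is linked to T:B here; no link is offered for bleeding, infection, flap loss or the others. A reader might take −7.5 points as the error of the planned model. That figure applies only to the BCT-specific effect, at the steepest assumed inputs, when the interaction (which the plan calls only possible) is fitted.

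**Conclusion.** The point holds as a cheap improvement to one secondary analysis. The text establishes the gap: section 7.1 suspects an effect independent of T:B ratio, the only complications model omits the ratio, and no planned model contains both terms. Bias is possible but not shown. It needs T:B to be associated with complications given group and W, on which the documents give no figure.

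Under the inputs in step 3 of the working, every spurious effect is below the protocol's 10-point threshold. For the BCT-specific effect it is still roughly 2.5/5.2 = 0.5 to 7.5/5.5 = 1.4 standard errors, enough to raise the false-positive rate. The documents do not support a stronger conclusion that the planned complication result will be wrong.

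**What to change.** In section 10.5.2, specify the complications model as Q-score on complication, group, group-by-complication, T:B ratio and group-by-T:B ratio, controlling for W, and report the complication effect from that model. Stating that W includes T:B would cover the main term but not group-by-T:B, which is needed because the protocol expects T:B to act mainly in BCT.

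The cost is one line of text and two model terms. T:B ratio is already planned study data (sections 6.2 and 8.0), and the loss of precision is almost nil. If T:B proves unrelated to complications, the estimate is essentially unchanged.

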1.2 Rationale

This study will show that many patients currently selected for lumpectomy will have better aesthetic outcomes when mastectomy with reconstruction is chosen. While the absolute dimensions of a breast cancer are relevant to staging and treatment, tumor: breast ratio is a key factor in determining patient satisfaction with lumpectomy, and in turn should determine when a mastectomy with reconstruction should be performed to yield an optimal result. It is the relative size of the tumor and volume of its resection that will profoundly impact breast symmetry and therefore impact patient reported outcomes following BCT. Tumor: breast ratios > 0.2 will be associated with progressively poorer patient satisfaction outcomes when treated with BCT than would be provided by mastectomy with reconstruction. Tumors in the superomedial breast will be even more sensitive to tumor: breast ratio. We hypothesize that BCT will be particularly sensitive to tumor: breast ratio whereas mastectomy with reconstruction will be less dependent. The results from this study will enable plastic and oncologic surgeons to identify a new cohort of patients, previously destined for BCT, to undergo a mastectomy with reconstruction to optimize their overall satisfaction with the aesthetic outcomes with equivalent treatment of their disease.

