2.2 Secondary Objectives

- Does tumor location impact the influence of tumor: breast ratio on patient reported outcomes following mastectomy with reconstruction or BCT?
- How does the pre and post-op Breast Q for the two groups (mastectomy + recon vs. BCT) reflect the tumor: breast ratio as calculated from 3D images rendered from MRI utilizing software-based algorithms?
- How does the pre and post-op Breast Q for the two groups (mastectomy + recon vs. BCT) reflect the VECTRA 3D generated mammometrics?

- What is the impact of radiation in BCT on Breast Q (Q-score before and after radiotherapy) and VECTRA (breast volume, nipple position, total breast skin surface area before and after radiotherapy)?
- How do complications that arise from each scenario (mastectomy + recon) vs. BCT impact patient satisfaction?
- What is the impact of tumor location and obesity as independent determinants of patient satisfaction in the two groups (mastectomy + recon vs. BCT) relative to tumor: breast ratio?

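### The last secondary model ranks T:B ratio, location and obesity on coefficients pooled over both arms, although the question concerns each group and the plan expects the T:B effect to differ by arm

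*Combined protocol and SAP*

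**What the plan says.** Section 2.2 asks about tumor location and obesity "as independent determinants of patient satisfaction in the two groups (mastectomy + recon vs. BCT) relative to tumor: breast ratio". Section 10.5.2 repeats the question and answers it with a model whose terms are "group, T:B ratio, location, and obesity as the independent variables, controlling for W in the model". The instruction that follows is: "Obtain the standardized regression coefficients for location, obesity, and T:B ratio, and compare each other to determine their relative importance". No product term with group is listed.

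Elsewhere the plan treats the T:B effect as specific to the arm. Section 1.2 states: "We hypothesize that BCT will be particularly sensitive to tumor: breast ratio whereas mastectomy with reconstruction will be less dependent". It adds: "Tumors in the superomedial breast will be even more sensitive to tumor: breast ratio". Model 2, under the primary objective in section 10.5.1, uses "group, T:B ratio, and group-by-T:B ratio interaction as the independent variables, controlling for W in the model". In section 10.5.2, Model 3 adds a three-way term with location, and Model 4 and the complication model each allow a possible interaction with group.

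**The concern.** A group main effect lets the arms differ in mean Q-score. It does not let any factor act differently in the two arms. The model therefore yields one T:B, one location and one obesity coefficient, and so one ranking for both arms.

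If the hypothesis in section 1.2 is right, that single T:B coefficient describes neither arm. What is at stake is the answer to this objective: how T:B compares with location and obesity as a determinant after BCT, and how it compares after reconstruction.

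**Working it through.** **Figure in the plan.** The documents give no figure for this model. The only related one is 83 per arm (section 10.4), used here for the allocation. At d = 0.45, two-sided alpha 0.05 and power 0.80, a t-test needs 79 per arm. Dividing by the relative efficiency 3/π of the Wilcoxon-Mann-Whitney test under normality, before rounding up, gives 83. So the figure reproduces under that variant.

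**Step 1: what the pooled coefficient estimates.** For one outcome per patient and a linear model with a group term but no interaction:

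b_pooled = Σ(n_g · V_g · b_g) / Σ(n_g · V_g)

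Here b_g is the T:B slope in arm g and V_g is the variance of T:B in that arm given the other covariates. With n = 83 in both arms the sample sizes cancel. Slopes and variances by arm are assumptions, so they are varied. Entries are b_pooled as a fraction of the BCT slope:

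| Reconstruction slope ÷ BCT slope | Variance ratio (reconstruction ÷ BCT) 0.5 | 1 | 2 | 4 |
|---|---|---|---|---|
| 0 | 0.67 | 0.50 | 0.33 | 0.20 |
| 0.25 | 0.75 | 0.63 | 0.50 | 0.40 |
| 0.5 | 0.83 | 0.75 | 0.67 | 0.60 |

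Example: slope ratio 0 and variance ratio 2 give (1 + 2·0)/(1 + 2) = 0.33.

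These are raw slopes. A standardized coefficient also multiplies by the pooled SD of T:B, so unequal variances partly offset. With equal T:B means, the 0.20 entry becomes 0.20 × √((1 + 4)/2) = 0.32 of the BCT value before division by the outcome SD.

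**Step 2: does the order change?** Within one fit the outcome SD is common to all three factors, so the order depends only on |b| × SD of the factor. Assumed: BCT slope −75 per unit T:B, T:B SD 0.09 in both arms, location −5 points at 25% prevalence, obesity −4 points at 35% prevalence. Location and obesity effects are equal in both arms.

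- Location: 5 × √(0.25 × 0.75) = 2.17
- Obesity: 4 × √(0.35 × 0.65) = 1.91
- T:B in BCT: 75 × 0.09 = 6.75

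| Slope ratio | T:B, reconstruction | T:B, pooled | Place of T:B: BCT / pooled / reconstruction |
|---|---|---|---|
| 0 | 0.00 | 3.38 | first / first / last |
| 0.25 | 1.69 | 4.22 | first / first / last |
| 0.5 | 3.38 | 5.06 | first / first / first |

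To standardize, divide by the outcome SD, taking the SD of 20 in section 10.4 as the residual. For BCT this is √(400 + 6.75² + 2.17² + 1.91²) = 21.3, so T:B is −6.75/21.3 = −0.32. Using the average within-arm variance, the pooled values are −0.16, −0.20 and −0.24. The reconstruction values are 0.00, −0.08 and −0.16. Location is about −0.10 and obesity about −0.09 throughout.

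**Step 3: can the BCT order change too?** Yes, under a stronger location effect. Assume effects per SD of T:B 0.40 in BCT and 0 in reconstruction, location 0.25 in both arms, and residual SD 0.9. The pooled T:B effect is (0.40 + 0)/2 = 0.20, below location at 0.25, although T:B leads in BCT. In 4,000 simulated studies with 83 per arm, T:B ranked above location in about 32% with the pooled model, against about 84% with the BCT arm alone.

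**The case against.** - **Models 2 and 3 already give arm-specific T:B slopes.** This is so, and it confines the problem to one comparison. Neither model, however, is planned to set T:B against location and obesity by arm, so they do not answer this objective.
- **The wording may mean the combined sample, adjusted for group.** That reading is possible. For location and obesity, section 1.2 states no difference in main effect by arm, so the case for separate coefficients there rests on the wording of the objective alone. For T:B it also rests on the plan's own hypothesis.
- **Rankings by arm will be noisy.** This stands. Section 10.4 sizes the study for a two-group difference. In the Step 2 example at slope ratio 0.5, T:B truly leads in reconstruction, but came first in only about 47% of simulated studies with 83 per arm.
- **Stronger readings.** A reader might infer that the ranking must be wrong in both arms, or that the T:B effect is averaged away. The documents support neither. They give no slopes or T:B variances by arm. In the Step 2 example the pooled order matches BCT in all three cases and reconstruction in one, and the pooled T:B effect stays the largest of the three. The effect is diluted, not removed. Nor is the pooled slope simply the mean of the two: that needs equal T:B variances as well as equal arms.

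**Conclusion.** The point holds as a mismatch between one secondary objective, the plan's hypothesis and the model chosen. If the T:B slope is steeper in BCT, the pooled coefficient understates it for BCT and overstates it for reconstruction. The factor of one half applies only to equal arms, equal T:B variances and a zero reconstruction slope. The 0.20 to 0.83 range reflects assumed slope ratios of 0 to 0.5 and variance ratios of 0.5 to 4. The formula is for one outcome per patient; the weights may differ somewhat in the repeated-measures models of section 10.5.

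The importance ranking can be wrong for an arm, most clearly for reconstruction. Whether it is wrong for BCT as well depends on how large the location and obesity effects are. The objective is descriptive, with no decision rule attached, and the primary analysis is unaffected. This is a minor to moderate improvement.

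**What to change.** In section 10.5.2, add the group-by-T:B term of Model 2 to the model for the last objective. Report standardized coefficients for T:B, location and obesity separately for BCT and for mastectomy with reconstruction, either from arm-specific fits or by adding group-by-location and group-by-obesity terms as well. State which SDs are used for standardizing. Give confidence intervals and label the comparison as descriptive.

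The change is to the analysis text only and needs no new patients or data. With interactions, the model carries three more coefficients. The price is wider intervals and rankings that may not be stable at about 83 per arm, which the report should say.

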6.7 Criteria for Removal from Study

If the patient, at any time wishes to be removed from the study, they will be. This study does not propose any new interventions – it is an observational study of patients receiving normal, uninfluenced care for the treatment of breast cancer.

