10.2 Data Fields Recorded

- PATIENT VARIABLES: BMI, smoking history, patient age, race, previous history breast augmentation,
- CANCER VARIABLES: cancer stage, presence or absence of sentinel lymph node biopsy, receptor status, tumor location, multifocal
- RADIATION & CHEMOTHERAPY VARIABLES: radiation received, length of treatment, chemotherapy selected, complications causing radiation or chemotherapy delay or dose reduction
- BREAST VARIABLES: standardized breast measurements (sternal notch to nipple, IMF to nipple, maximum areolar diameter, ptosis)
- SURGICAL VARIABLES: patients undergoing mastectomy with reconstruction as per routine will be recorded as immediate implant, expander-reconstruction, use of acellular dermal matrix, or flap including predominantly DIEP, but also free TRAM, latissimus, PAP, SIEA, TUG, or SGAP. Also balancing procedures will be considered like breast reduction/lift/augmentation/augmentation with lift, fat grafting, adjacent tissue transfer, pseudohernia repair, correction of malposition, implant exchange, capsulectomy, capsulorrhaphy, Ryan procedure,
- IMAGING VARIABLES: tumor: breast ratio, mammometrics (breast volumes, surface area, nipple position, chest wall morphology, vectors, anatomic landmarks)
- COMPLICATION VARIABLES: complications related to breast surgery will be recorded (anesthetic complications, bleeding, infection requiring readmission or surgery, wound healing problems requiring surgical intervention, need for re-excision in lumpectomy due to positive margins, and reconstructive failures due to flap loss or breast prosthesis explant). Patients with complications will be included as this is a key determinant of patient reported outcomes.

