10.4 Sample Size

Mammometrics will be converted to comparable data and then related to Q-Score as these are expected to be complex relationships.

We anticipate enrolling 83 subjects per study arm (166 total) with up to an additional 20 subjects undergoing mastectomy without reconstruction as a negative control for a total of 186 patients.

Initial plan is to use G*Power v 3.1, or a comparable statistical package. Based on an effect size $d=0.45$, Type I error $\alpha=0.05$, and power $(1-\beta) =0.8$, normal distribution, and 2-tails, we will require 83 subjects per arm (166 total). Assumptions: A difference in mean scores of 10 on a 100-point scale (Q-Score generated from Breast Q) was assumed to be significant. This is determined by assuming an SD of 20, with one-half of an SD being the threshold of discrimination for change in health-related quality of life.

Sample size calculations are based on 1) previously reported sample size calculations where data from the Breast Q for Breast Reconstruction was used with 2) the open-source statistical package G*Power 3.1.

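### Ranking location, obesity and T:B ratio by standardized coefficients mixes effect size with the case mix enrolled, and the plan gives no interval for the differences being ranked

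*Combined protocol and SAP*

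**What the plan says.** The last objective in Section 10.5.2 asks how tumor location and obesity act as determinants of satisfaction relative to T:B ratio. The model has Q-score as outcome, with group, T:B ratio, location and obesity as predictors and adjustment for W. The ranking rule is: "Obtain the standardized regression coefficients for location, obesity, and T:B ratio, and compare each other to determine their relative importance".

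On how the three factors are measured:

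- Location, Section 10.5: "location is a binary indicator of tumor location".
- T:B ratio, Section 10.5: "T:B ratio is the tumor: breast ratio measured at a continuous scale". No SD or expected range among enrolled women is given.
- Obesity: no coding or cut-off is stated. Section 10.5 names it among the examples of W ("e.g., age, obesity, stage, etc"), and Section 10.2 records BMI ("PATIENT VARIABLES: BMI, smoking history, patient age, race").

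The plan gives no expected share of women for location or obesity. It states no interval or test for differences between the standardized coefficients, and no other measure of importance.

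**The concern.** Standardizing puts the three factors on a common scale by multiplying each effect by that factor's own SD in the sample. For a yes/no factor the SD is fixed by its prevalence; for T:B or BMI it is the spread enrolled. Two studies with identical effects in Q points but a different mix of women could therefore report different orders.

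The rule also moves directly from three estimates to a statement of relative importance, with no account of how precisely their differences are known.

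Section 1.2 expects the results to help surgeons identify women for one operation rather than the other. A stated order of T:B, location and obesity would be read in that light, and an order that partly reflects case mix need not carry over to another practice.

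**Working it through.** **Inputs from the plan (Section 10.4).** SD of Q-score 20 ("This is determined by assuming an SD of 20"); difference of interest 10 points; 83 women per arm, 166 in the two compared arms. The 83 can be reproduced: d = 0.45, two-sided alpha 0.05 and power 0.80 give 78.5 per arm by t-test, and 78.5/0.955 = 82.2, so 83, for the rank-test variant with a normal parent distribution. That figure is not in dispute and is used here only for precision.

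**Assumed inputs, because the plan gives none.** The prevalences, the T:B slope, the SD of T:B and the 8-point obesity effect used below.

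**1. Yes/no factor.** Standardized coefficient = b × sqrt(p(1−p)) / SD(Q). With b = 10 and SD(Q) = 20:

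| Prevalence p | sqrt(p(1−p)) | Standardized coefficient |
|---|---|---|
| 10% | 0.300 | 0.150 |
| 20% | 0.400 | 0.200 |
| 30% | 0.458 | 0.229 |
| 40% | 0.490 | 0.245 |
| 50% | 0.500 | 0.250 |

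The effect is 10 points in every row. From 10% to 50% the coefficient rises by a factor of 0.25/0.15 = 1.67. From 30% to 50% it rises by 0.250/0.229 = 1.09, about 9%.

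**2. T:B ratio.** Standardized coefficient = slope × SD(T:B) / SD(Q). A slope of 5 points per 0.1 is 50 per unit. This gives 50 × 0.05/20 = 0.125, or 50 × 0.10/20 = 0.25. T:B would fall below the 10% row of the table in one case and level with the 50% row in the other.

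**3. Reversal of order.** Take location = 10 points and obesity = 8 points, both yes/no.

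- Prevalence 10% and 40%: 0.150 against 8 × 0.490/20 = 0.196. Obesity comes first.
- Prevalence 40% and 20%: 0.245 against 8 × 0.400/20 = 0.160. Location comes first.

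**4. Sampling error.** With 166 women, one score each, complete data, a small R-squared and nearly uncorrelated predictors, the standard error of a standardized coefficient is about 1/sqrt(166) = 0.078. For the difference of two uncorrelated coefficients it is sqrt(2) × 0.078 = 0.110, so the 95% half-width is 1.96 × 0.110 = 0.22. The gap between 0.25 and 0.15 is 0.10, well inside that.

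**5. Simulation.** There were 4,000 samples of 166 for each setting, with residual SD 20, true effects of 10 points (location) and 8 points (obesity), T:B mean 0.12 and SD 0.06. The table shows how often location ranked above obesity:

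| Prevalence, location / obesity | By standardized coefficient | By Q points |
|---|---|---|
| 10% / 40% | 33% | 63% |
| 20% / 40% | 53% | 66% |
| 30% / 30% | 67% | 67% |
| 40% / 20% | 78% | 66% |

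The standardized order follows prevalence. The order in Q points does not, but it is still wrong in about a third of samples, so any order needs an interval.

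**The case against.** **Standardization answers a real problem.** A slope and a yes/no contrast share no unit. In Q points the assumed T:B slope is 5 points per 0.1 but 10 points per 0.2, so its place against a yes/no factor depends on the step chosen. Importance across the women enrolled, where prevalence legitimately counts, is also one reading of relative importance. This stands. It means standardized coefficients may be kept if labelled for what they are, and that the steps for Q-point contrasts must be fixed beforehand.

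**Raw effects come with the model anyway.** True, since fitting it yields coefficients with standard errors. But the plan makes the comparison of standardized coefficients the basis for the conclusion, and nothing requires the raw effects or the precision of the differences to be reported with it.

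**Some stronger readings go beyond the documents:**

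- A reader might infer that the ranking is an artefact of sampling. Dependence on case mix is the exact description. Chance variation in prevalence at n = 166 moves a 10-point effect over 0.113 to 0.176 for a true 10% and 0.173 to 0.221 for a true 20%. That is modest, and no larger than the ordinary error of the coefficient.
- A reader might infer two yes/no factors. Only location is stated to be binary. If BMI is entered as continuous, its coefficient depends on the spread of BMI instead.
- A reader might infer that recruitment quotas set the spread of T:B. No quota by T:B, location or obesity is described; Section 6.7 says "it is an observational study of patients receiving normal, uninfluenced care for the treatment of breast cancer".
- A reader might take the listing of obesity both in W and as its own term as a modelling error. W is a list of examples and one term is the natural reading. The wording needs tidying, no more.

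**Conclusion.** The point holds as a matter of case-mix dependence and missing precision. With effects held fixed, a yes/no factor's standardized coefficient can differ by a factor of 1.67 between 10% and 50% prevalence, and that of T:B doubles if its SD doubles. Differences of this size are comparable with the sampling error of a difference, about 0.11. Nothing in the plan stops an order being declared from three point estimates.

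The SD of 20 and the 166 women are the plan's figures. The prevalences, slope, T:B SDs and obesity effect are assumptions. If location and obesity both turn out to lie between 30% and 50%, the prevalence effect is minor and noise is the main concern. The standard errors assume complete data and nearly uncorrelated predictors.

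A reader might extend this to the primary objective or the sample size. The documents do not support that: Models 1 and 2 and the calculation in Section 10.4 do not use this ranking. One secondary objective is affected, and the improvement is cheap and worth making.

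**What to change.** Replace the ranking sentence in Section 10.5.2 as follows.

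1. Report each factor's effect in Q points for a contrast fixed before analysis (location yes against no, a stated BMI step, T:B per 0.1), each with a 95% CI.
2. State how obesity is coded, and enter obesity or BMI once in this model.
3. If standardized coefficients are kept, label them as importance in this sample only. Give bootstrap CIs for the pairwise differences in absolute size, resampling women so that repeated scores stay together, and claim an order only when the interval excludes zero.

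Loss of explained variance when a factor is dropped should not be used as the remedy. In linear regression it equals the squared standardized coefficient times the predictor's tolerance. With tolerance 1, the same 10-point effect gives 0.15² = 0.0225 at 10% prevalence and 0.25² = 0.0625 at 50%, a 2.8-fold change, so the dependence is larger.

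The cost is a change of wording and, if needed, a bootstrap; no new data are required. There are two downsides. An order in Q points depends on the T:B and BMI steps, which is why they must be set in advance, and the analysis may end with no ranking claimed.
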